8.1.2. Clinical Laboratory Evaluations

The laboratory assessments include

- Hematology

- Urinalysis with microscopic examination
- Serum chemistry
- Liver panel
- Circulating AFP level.

All summaries will be based on the SI units, and missing values will not be imputed. Summary statistics of the observed values and change from baseline for all laboratory parameters except for Urinalysis, will be provided at the scheduled visits. The number and percentage of subjects with shift on extreme post-baseline values in low/normal/high from baseline will be presented in a shift table for selected laboratory parameters. Extreme laboratory value is the lowest or highest category a patient has post-baseline for the laboratory parameters. If a patient has a value below the normal range and a value above the normal range, the value furthest from the normal range will be chosen.

All laboratory data will also be presented in listings for each summary section with abnormal values flagged.

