**Exclusion Criteria**

	

1. Known to be unresponsive to ERT.

2. Neutralizing antibodies in serum (immune response) to AAV2/6.

3. Serious intercurrent illness or clinically significant organic disease (unless secondary to MPS I) such as cardiovascular, hepatic, pulmonary, neurologic, or renal disease.

4. Receiving antiviral therapy for hepatitis B or C, or with active hepatitis B (HBV DNA positive or HBV surface antigen positive) or hepatitis C (HCV RNA viral load) or human immunodeficiency virus (HIV)-1/2 (HIV RNA viral load or HIV antibody positive); to be considered negative for hepatitis C after treatment of an active HCV infection, viral assays in 2 samples collected at least 6 months apart must be negative.

5. Lack of tolerance to ERT with significant infusion-associated reactions (IARs) or occurrence of anaphylaxis.

6. Polymorphisms in the ZFN-targeted region of the albumin locus.

7. Liver fibrosis score of 3 or 4 on a 0 to 4 point scale (Desmet et al. 1994) if subject has had a liver biopsy within 2 years of Screening.

8. Markers of hepatic dysfunction as evidenced by one or more of the following:

a. Platelet count <100,000/<math>\mu</math>L.

b. Albumin <math>\leq</math>3.2 g/dL.

c. Total bilirubin <math>></math>1.5 x upper limit of normal (ULN) and direct bilirubin <math>\geq</math>0.5 mg/dL.

d. Alkaline phosphatase <math>></math>2.0 x ULN.

e. Alanine aminotransferase (ALT) or aspartate aminotransferase (AST) <math>></math>2.0 x ULN.

9. Creatinine <math>\geq</math> 1.5 mg/dL.

10. Weight <math><</math> 20 kg at Screening.

11. Pregnant or breastfeeding female.

12. Contraindication to the use of corticosteroids.

--	---

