### **13.4 Primary Endpoint**

The primary endpoint of this study is the incidence of treatment-emergent AEs (including SAEs). Additional safety evaluations will include:

- Routine hematology, chemistry, and liver function laboratory tests, vital signs, physical exam, ECG, ECHO, and concomitant medications.
- Monitoring of chimerism in post-HSCT subjects.
- Cranial nerve exam and muscle strength testing.
- Serial AFP testing and MRI of liver to evaluate for liver mass.

Safety assessment will be performed on all subjects. All reported AEs will be coded to a standard set of terms using the Medical Dictionary for Regulatory Activities (MedDRA).

Treatment-emergent adverse events will be summarized overall and by treatment cohort. For each subject, the maximum reported severity of each adverse event will be used in the summaries by severity grade. In addition, all serious adverse events and AEs related to study treatment will be summarized.

Laboratory data will be summarized for each time-point at which specimens are collected. Change-from-Baseline values may be calculated for selected laboratory parameters. Shift-tables (Change-from-Baseline relative to the normal range) may be constructed for selected laboratory parameters.

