## APPENDIX 3: IMMUNOSUPPRESSION REGIMEN

Weight of Subject (kg)	Oral Prednisone (mg/day)					
	Day -2 to Day 0	Week 1	Week 2	Week 3-16	Week 17-19	Week 20
≥ 60	60	60	30	15	5	STOP
55	60	60	30	15	5	STOP
50	50	50	25	15	5	STOP
45	45	45	25	15	5	STOP
40	40	40	20	10	5	STOP
35	35	35	20	10	5	STOP
30	30	30	15	10	5	STOP
<30	1 mg/kg	1 mg/kg	0.5 mg/kg	0.25 mg/kg	0.25 mg/kg every other day	STOP

Prednisone or equivalent corticosteroid regimen is commenced 2 days prior to Day 0 of SB-318 infusion and given once daily unless otherwise stated. Subject's liver function will be monitored twice a week while on prednisone or equivalent corticosteroid. Blood for liver panel shall be drawn 2 to 4 days apart when possible, except for the first week when it will be drawn on the Day 1 and Day 7 visits. Tapering of prednisone or equivalent corticosteroid will only proceed if ALT/AST activity levels are stable or declining (based on the 2 assessments of the preceding week).

If subjects develop increased ALT > 2 fold Baseline while on prednisone or equivalent corticosteroid or after stopping prednisone or equivalent corticosteroid, the prednisone or equivalent corticosteroid regimen may be adjusted or restarted at the Principal Investigator's discretion after consultation with the Medical Monitor.

Twice a week liver panel testing should continue until the prednisone or equivalent corticosteroid course has been terminated.

An ACTH stimulation (cosyntropin) test will be performed prior to the first prednisone or equivalent corticosteroid dose and again during Week 20 or at the end of the scheduled taper to ensure that the adrenal cortical function has not been suppressed. Should prednisone or equivalent corticosteroid treatment be repeated due to increased transaminase activity, the ACTH stimulation test will be repeated at the end of taper at the Principal Investigator's discretion.

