MEAN (SD)	xx.x (xx.xx)		xx.x (xx.xx)		xx.x (xx.xx)	
MEDIAN	xx.x		xx.x		xx.x	
MIN, MAX	xx, xx		xx, xx		xx, xx	
VISIT X						
n	xx	xx	xx	xx	xx	xx
MEAN (SD)	xx.x (xx.xx)	xx.x (xx.xx)	xx.x (xx.xx)	xx.x (xx.xx)	xx.x (xx.xx)	xx.x (xx.xx)
MEDIAN	xx.x	xx.x	xx.x	xx.x	xx.x	xx.x
MIN, MAX	xx, xx	xx, xx	xx, xx	xx, xx	xx, xx	xx, xx

Note: Baseline is defined as last non-missing measurement prior to dosing.

[1]Change from baseline: post-baseline value - baseline value. For the change from baseline, only subjects with a value at both baseline visit and the specific post-baseline visit are included.

Source Data: Listing 16.2.8.1.3

<DIRECTORY PATH>PROGRAM NAME Executed: DDMMYYYY hh:mm

Prog Note: Lab test parameters will be displayed in the same order as the lab test listing.
Include all post-baseline visits.

Table 14.3.4.3
Change from Baseline in Circulating Alpha Fetoprotein Level (ng/mL)
Safety Set

Visit	SB-318 1.00E+13 vg/kg (N=xx)		SB-318 5.00E+13 vg/kg (N=xx)		Total (N=xx)	
	Actual Value	Change From Baseline [1]	Actual Value	Change From Baseline [1]	Actual Value	Change From Baseline [1]
BASELINE						
n	xx		xx		xx	
MEAN (SD)	xx.x (xx.xx)		xx.x (xx.xx)		xx.x (xx.xx)	
MEDIAN	xx.x		xx.x		xx.x	
MIN, MAX	xx, xx		xx, xx		xx, xx	
VISIT X						
n	xx	xx	xx	xx	xx	xx
MEAN (SD)	xx.x (xx.xx)	xx.x (xx.xx)	xx.x (xx.xx)	xx.x (xx.xx)	xx.x (xx.xx)	xx.x (xx.xx)
MEDIAN	xx.x	xx.x	xx.x	xx.x	xx.x	xx.x
MIN, MAX	xx, xx	xx, xx	xx, xx	xx, xx	xx, xx	xx, xx

Note: Baseline is defined as last non-missing measurement prior to dosing.

[1]Change from baseline: post-baseline value - baseline value. For the change from baseline, only subjects with a value at both baseline visit and the specific post-baseline visit are included.

Source Data: Listing 16.2.8.1.4

<DIRECTORY PATH>PROGRAM NAME Executed: DDMMYYYY hh:mm

Prog Note: The post-baseline visits include Weeks 4, 8, 12, 24, 48, Months 18, 24, 30, 36/EOS, or Early Termination Visit if applicable.

Table 14.3.4.4
Shift from Baseline to Worst Post-Baseline for Laboratory Parameters - Serum Chemistry
Safety Set

Parameter: LAB TEST #1 (UNIT)

Cohort	Baseline Value	Extreme Value [1]			
		Baseline n (%)	Low n (%)	Normal n (%)	High n (%)
SB-318 1.00E+13 vg/kg (N=xxx)					
Low	xx (xx.x)	xx (xx.x)	xx (xx.x)	xx (xx.x)	xx (xx.x)
Normal	xx (xx.x)	xx (xx.x)	xx (xx.x)	xx (xx.x)	xx (xx.x)
High	xx (xx.x)	xx (xx.x)	xx (xx.x)	xx (xx.x)	xx (xx.x)
Total	xx (xx.x)	xx (xx.x)	xx (xx.x)	xx (xx.x)	xx (xx.x)
SB-318 5.00E+13 vg/kg (N=xxx)					

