Low	xx (xx.x)	xx (xx.x)	xx (xx.x)	xx (xx.x)	xx (xx.x)

...
Note: Baseline is defined as last non-missing measurement prior to dosing.

Counts represent patients with a baseline value in addition to having at least one value at post-baseline visits. Baseline percentage is based on N. Percentage for extreme value is based on Baseline n.

'Low' denotes a value below the normal range. 'High' denotes a value above the normal range.

[1] Extreme laboratory value is the lowest or highest category a patient has post-baseline for the laboratory parameter. If a patient has a value below the threshold and above the threshold, the value furthest from the threshold will be chosen.

Source Data: Listing 16.2.8.1.3

<DIRECTORY PATH>PROGRAM NAME Executed: DDMMYYYY hh:mm

Table 14.3.4.5
Shift from Baseline to Worst Post-Baseline for Laboratory Parameters - Hematology
Safety Set

Parameter: LAB TEST #1 (UNIT)

Cohort	Baseline Value	Extreme Value [1]		
		Low n (%)	Normal n (%)	High n (%)
SB-318 1.00E+13 vg/kg (N=xxx)				
Low	xx (xx.x)	xx (xx.x)	xx (xx.x)	xx (xx.x)
Normal	xx (xx.x)	xx (xx.x)	xx (xx.x)	xx (xx.x)
High	xx (xx.x)	xx (xx.x)	xx (xx.x)	xx (xx.x)
Total	xx (xx.x)	xx (xx.x)	xx (xx.x)	xx (xx.x)
SB-318 5.00E+13 vg/kg (N=xxx)				
Low	xx (xx.x)	xx (xx.x)	xx (xx.x)	xx (xx.x)
...				

Note: Baseline is defined as last non-missing measurement prior to dosing.

Counts represent patients with a baseline value in addition to having at least one value at post-baseline visits. Baseline percentage is based on N. Percentage for extreme value is based on Baseline n.

'Low' denotes a value below the normal range. 'High' denotes a value above the normal range.

[1] Extreme laboratory value is the lowest or highest category a patient has post-baseline for the laboratory parameter. If a patient has a value below the threshold and above the threshold, the value furthest from the threshold will be chosen.

Source Data: Listing 16.2.8.1.1

<DIRECTORY PATH>PROGRAM NAME Executed: DDMMYYYY hh:mm

Table 14.3.5
Change from Baseline in Vital Signs
Safety Set

Parameter: VITAL SIGN PARAMETER #1 (UNIT)

Visit Timepoint	SB-318 1.00E+13 vg/kg (N=xx)		SB-318 5.00E+13 vg/kg (N=xx)		Total (N=xx)	
	Actual Value	Change From Baseline [1]	Actual Value	Change From Baseline [1]	Actual Value	Change From Baseline [1]
BASELINE						
n	xx		xx		xx	
MEAN (SD)	xx.x (xx.xx)		xx.x (xx.xx)		xx.x (xx.xx)	
MEDIAN	xx.x		xx.x		xx.x	
MIN, MAX	xx, xx		xx, xx		xx, xx	
DAY 0						
MAXIMUM						
n	xx	xx	xx	xx	xx	xx

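### No planned table shows a subject's peak ALT/AST over all draws, or as a multiple of Baseline or ULN, and liver panels drawn between visits have no assigned place

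*SAP*

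**What the plan says.** SAP 8.1.2 plans two kinds of laboratory table.

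- **By visit:** "Summary statistics of the observed values and change from baseline for all laboratory parameters except for Urinalysis, will be provided at the scheduled visits". SAP section 4 sets the statistics as n, mean, SD, median, minimum and maximum.
- **Worst value:** "subjects with shift on extreme post-baseline values in low/normal/high from baseline will be presented in a shift table for selected laboratory parameters". The selected parameters are not named. For a patient who has been out of range in both directions, SAP 8.1.2 gives a single-value rule: "a value below the normal range and a value above the normal range, the value furthest from the normal range will be chosen".

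Three other texts bear on which draws count.

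- Protocol 13.4: "Laboratory data will be summarized for each time-point at which specimens are collected".
- The programming note to shell Table 14.3.4.2 (serum chemistry): "Include all post-baseline visits".
- The footnote to shell Tables 14.3.4.4 and 14.3.4.5: "Extreme laboratory value is the lowest or highest category a patient has post-baseline for the laboratory parameter". The same footnote restricts the counts to patients with a Baseline value and at least one value at a visit after Baseline.

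Protocol 3.5 and 9.13 call for liver panels twice a week for 20 weeks, 2 to 4 days apart where possible (Day 1 and Day 7 in the first week), and allow remote collection. Protocol Appendix 3 uses a relative ALT level: "If subjects develop increased ALT > 2 fold Baseline while on prednisone or equivalent corticosteroid".

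For the liver MRI, SAP 3.2.1 gives liver mass as the purpose of the safety evaluation. SAP 8.1.10 and shell Table 14.3.10 count scans as normal or abnormal.

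**The concern.** Safety is the primary objective. Transaminitis heads the key risks in protocol 12.2, and SAP 3.1 says the twice-weekly panels are there to evaluate immune reaction to the vector. The natural safety question is how high each subject's ALT and AST went, relative to that subject's own Baseline and to ULN. No planned table answers it.

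The worst-value display keeps only a category. Eligibility excludes ALT or AST only above 2.0 x ULN, so a subject can start above normal and stay High to High whatever the rise. A subject starting low in the normal range can pass the protocol's own 2-fold level and read as unchanged. The by-visit tables carry size, but on the narrow reading most of the intensive sampling does not reach them. A reader would then have to rebuild each subject's peak from the listings.

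The SAP handles a similar problem elsewhere. For repeated vital signs on Day 0, section 8.1.3 reports each subject's maximum and minimum.

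**Working it through.** The plan gives no figure to reproduce here. The study is descriptive, so the check is a count of draws and a test of what each table can display.

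**Panels per subject to Week 20** (protocol 3.5, 9.13)
- Week 1: Day 1 and Day 7 = 2.
- Weeks 2 to 20: 2 x 19 = 38.
- Total: 2 + 38 = 40.

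**Panels on a scheduled visit** (protocol 6.5 to 6.8)
- Day 1, Day 7, Weeks 2, 4, 6, 8, 12, 16 and 20 = 9.

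**Panels outside every by-visit table**
- SAP 8.1.2 governs, read narrowly: 40 - 9 = 31, and 31/40 = 77.5%.
- Protocol 13.4 governs: 0.
- On the narrow reading, tabulated values lie 14 days apart from Week 2 to Week 8 and 28 days apart from Week 8 to Week 20.

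**Weeks 2 to 9**, the period in which protocol 3.5 says transaminitis occurred in AAV8 Factor IX studies. It contains 4 visits (Weeks 2, 4, 6, 8).
- Counted as 7 elapsed weeks: 14 - 4 = 10 draws between visits (71%).
- Counted as 8 study weeks: 16 - 4 = 12 (75%).

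**What the shift table can separate** (assumed values; the documents give no ULN)
- ULN 40, Baseline 30: peaks of 41, 61, 201 and 801 all fall in the Normal-to-High cell. They run from 41/40 = 1.02 to 801/40 = 20.0 x ULN, and from 41/30 = 1.4 to 801/30 = 26.7 x Baseline.
- Baseline 1.5 x ULN, peak 3.5 x ULN: 3.5/1.5 = 2.3-fold, shown as High to High.
- Baseline 0.45 x ULN, peak 0.95 x ULN: 0.95/0.45 = 2.1-fold, shown as Normal to Normal. This pattern requires a Baseline below 0.5 x ULN.

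The documents give no CTCAE cut-offs, so none of these examples is assigned a grade.

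**What the by-visit table can show**
- Two subjects, both with Baseline 30 and visit values 200 and 35: the table prints a maximum of 200 and a maximum change of 200 - 30 = +170. Size is visible when the rise is present at a visit.

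**Liver MRI visits after Baseline**
- SAP 8.1.10: Week 48, Months 24 and 36.
- Protocol 6.8 and 6.9, and shell Table 14.3.10: Weeks 24 and 48, Months 18, 24, 30 and 36. The SAP text names 3 of these 6.

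**The case against.** A reader might infer that the planned tables cannot show the size of an ALT or AST rise at all. The documents do not support that. The by-visit tables give minimum, maximum and change in absolute units. The shells have only two dose columns, for cohorts planned at 1 and 2 subjects, so those extremes are close to individual values. Only the shift table is blind to size.

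A reader might also infer that three quarters of the liver panels are lost. The figure of 31 is an upper bound that comes from unclear wording. Under protocol 13.4 it is zero, and every result is listed with its normal range and a flag.

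Nor can one say that the shift table takes in peaks between visits, or that it leaves them out. SAP 8.1.2 speaks only of values after Baseline, while the shell footnote speaks of values at visits.

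Much of what matters clinically has another route. Protocol 10.3 makes worsening Grade 3-4 results adverse events unless they belong to a diagnosis already reported. Protocol 10.1.1 does the same for abnormalities that are clinically significant or need medication. Corticosteroids are recorded as concomitant medication. To go unseen in the tables, a rise would have to peak between visits, fade before the next one, be Grade 1-2, and be neither judged significant nor treated.

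On the MRI, a reader might infer that a new mass would not alter the table. That depends on whether organ enlargement is recorded as abnormal, which the SAP does not say. SAP 8.1.10 opens with liver mass and 8.3.5 handles volumes separately, so the mass reading is a fair one. Findings are listed, and protocol 9.30 sends suspicious masses or those over 2 cm to biopsy.

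These points narrow the concern and lower its severity. They do not supply a peak or fold-change table, or a rule for draws between visits.

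**Conclusion.** The point holds in limited form, at minor to moderate severity. No planned table gives a subject's peak ALT or AST over all draws, or as a multiple of Baseline or ULN. SAP 8.1.2 and protocol 13.4 differ on which draws are summarised, and SAP section 11, which lists changes from the protocol's statistical section, does not mention this one. Between 0 and 31 of 40 planned panels per subject are affected, depending on which text governs.

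Harm is limited because the listings hold the values and the study is small: 1 + 2 x 6 = 13 planned subjects, and at most 13 + 2 x 7 = 27.

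The conclusion assumes the planned draw schedule is followed and that liver-panel results are reported in the serum chemistry tables. That placement is implied only: no shell is titled liver panel, and the serum chemistry column of protocol Table 1 does not list ALT or AST. Outputs for the Safety Monitoring Committee are in a separate document and may already contain such a display. The MRI part is a matter of clarity, not a shown failure.

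**What to change.** 1. Add a table with one row per subject giving maximum ALT, AST and bilirubin as multiples of Baseline and of ULN, using every draw after Baseline, remote and unscheduled ones included. Add a count of subjects above 2 x Baseline ALT, for reporting only; it changes no clinical rule.
2. Align SAP 8.1.2 with protocol 13.4. State that draws between visits enter the shift tables, and give the window by which they enter the by-visit tables. Make the shell notes and footnotes agree.
3. Show shifts to the lowest and to the highest category separately, so that one direction does not hide the other. This matters for parameters other than ALT and AST.
4. In Table 14.3.10, report liver mass present or absent from the recorded findings, or state that abnormal means a mass. Reconcile the visits in SAP 8.1.10 with the protocol and the shell.

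Cost: SAP and shell wording, one table of 13 to 27 rows, split shift tables and one MRI row, which means a few more output pages. No new data are needed, although mass present or absent would have to be read from free-text findings.

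### The laboratory shift tables keep one direction per subject by an undefined distance, so a high value can displace a proportionally worse low

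*SAP*

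**What the plan says.** SAP 8.1.2 (Clinical Laboratory Evaluations) plans a "shift on extreme post-baseline values in low/normal/high from baseline will be presented in a shift table for selected laboratory parameters". A subject contributes one extreme category per parameter. When post-baseline values lie on both sides of the normal range, "the value furthest from the normal range will be chosen".

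The shells carry the rule into Table 14.3.4.4 ("Shift from Baseline to Worst Post-Baseline for Laboratory Parameters - Serum Chemistry") and Table 14.3.4.5 ("Shift from Baseline to Worst Post-Baseline for Laboratory Parameters - Hematology"), with a change of noun: "If a patient has a value below the threshold and above the threshold, the value furthest from the threshold will be chosen". The footnotes define Low and High against the normal range but do not say what the threshold is.

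The nearest statement about scale, also in SAP 8.1.2, is "All summaries will be based on the SI units, and missing values will not be imputed". That fixes the reporting units. It does not say how distance is measured.

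The same section then adds: "All laboratory data will also be presented in listings for each summary section with abnormal values flagged".

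**The concern.** The tables are titled as a shift to the worst post-baseline value, but distance from the range does not establish which of two opposite abnormalities is worse. Three things follow.

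- One of the two directions is always dropped from the table for a subject who has both.
- Which one is dropped depends on a metric that the programmer must choose. Two programmers following the SAP could place the same subject in opposite cells.
- On the most natural metric, the plain difference in reported units, the choice is not symmetric: a low excursion is bounded by zero and a high excursion is unbounded.

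Laboratory tests are among the safety evaluations listed with the primary endpoint (SAP 3.2.1), and these two tables are the only Low/Normal/High tabulation in the shells. What is at stake is whether that tabulation shows every direction of abnormality that occurred.

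**Working it through.** The plan gives no figure to reproduce, so the check is of the rule itself.

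**Inputs.** The rule comes from SAP 8.1.2 and the two shell footnotes. The documents give no normal ranges for hematology or chemistry parameters, so every range below is an assumption. The SAP does not name the selected parameters. Protocol Table 1 includes a platelet count and glucose, so both are candidates.

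**Raw distance.** Write LLN and ULN for the limits of normal, L for the low value and H for the high value.

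- Low distance = LLN − L. Since L ≥ 0, this is at most LLN.
- High distance = H − ULN, which has no upper bound.
- High is kept when H − ULN > LLN − L. Any H above ULN + LLN therefore outranks every low, even zero.

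Changing units multiplies both distances by the same factor, and so does dividing by the width of the range. Neither changes the choice. Dividing each distance by its own limit can change it.

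**Example, assumed platelet limits 150–400, values 45 and 520 in one subject.**

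| Metric | Low | High | Category kept |
|---|---|---|---|
| Raw distance | 150 − 45 = 105 | 520 − 400 = 120 | High |
| Percent of limit | 105/150 = 70% | 120/400 = 30% | Low |
| Fold of limit | 150/45 = 3.33 | 520/400 = 1.30 | Low |

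The raw-distance switch point is H = 400 + 105 = 505. With a high of 500 the distances are 105 and 100, and Low is kept on all three metrics.

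**How far this depends on the range.** Let R = ULN/LLN and L = f × LLN. High wins on raw distance once H exceeds ULN by more than (1 − f)/R, as a fraction of ULN.

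| R | Low at 10% of LLN | Low at 50% of LLN |
|---|---|---|
| 1.1 | 81.8% | 45.5% |
| 1.5 | 60.0% | 33.3% |
| 2 | 45.0% | 25.0% |
| 3 | 30.0% | 16.7% |
| 4 | 22.5% | 12.5% |
| 10 | 9.0% | 5.0% |

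Entries are the excess of the high over ULN needed to displace the low. The effect is strong for wide ranges and weak for narrow ones.

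**Highs that outrank every non-zero low (H = ULN + LLN), assumed ranges.** White cells 4–11: 11 + 4 = 15, which is 4/11 = 36% above ULN. Glucose 3.9–6.1 mmol/L: 6.1 + 3.9 = 10.0, which is 3.9/6.1 = 64% above ULN.

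**The case against.** A reader might infer that a modest high erases a clinically severe low, and that cytopenia or hypoglycaemia would vanish from the laboratory safety reporting. The documents do not support that, for four reasons.

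1. **Raw distance is not written.** It is the natural reading, but percent-of-limit or fold would keep the low in the platelet example. What the text establishes is that the metric is undefined.
2. **The loss is conditional.** It needs both excursions in the same subject and parameter, with a large enough high. For narrow ranges (R of 1.1 to 1.5) the high must be 60–82% above ULN to displace a low at 10% of LLN. The glucose figure of 64% above ULN is not modest. A low can also displace a high. Protocol 8.2 lists raised blood sugar as a steroid effect, which supports expecting high glucose, but it lists neither raised white cells nor raised platelets. The laboratory risks named in Protocol 12.2, transaminitis and reduced albumin synthesis, each concern one direction, so the rule operates only if an opposite excursion also occurs.
3. **Other routes carry the value.** All values are listed with flags. The by-visit shells show minimum and maximum, and with the planned one or two subjects per cohort these are the individual values. Under Protocol 10.3, a Grade 3–4 result that worsens from Baseline is recorded as an adverse event unless it belongs to a diagnosis already reported, and so reaches the graded adverse event tables.
4. **The tables are descriptive.** Protocol 13.4 makes shift tables optional for selected parameters, and the SAP tests no hypotheses.

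All four points limit the impact. They do not cure the rule, and the other routes are partial. Under Protocol 10.3, Grade 1–2 laboratory results become adverse events only if judged clinically significant. The shell note for the by-visit hematology table omits Month 33, and an unscheduled hematology value may appear only in the listing. Protocol Section 6 schedules 19 post-baseline clinical laboratory visits for a subject who completes 36 months (Day 1, 4 in Weeks 2–8, 6 in Weeks 12–48, 8 in Months 15–36), so opposite excursions in one subject are possible, though nothing shows that they are expected.

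**Conclusion.** The point holds in a limited form. The rule discards one direction of abnormality from a table headed as worst post-baseline, by a distance that neither SAP 8.1.2 nor the shells define. On raw distance it favours highs, and for wide ranges a high can displace a proportionally worse low: 45 and 520 against assumed limits of 150–400 give High on raw distance and Low on percent of limit.

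The consequence is confined to the shift tables. A displaced value may be absent there, but it remains in the flagged listings, usually in the by-visit minimum and maximum, and in adverse event reporting when it is a worsening Grade 3–4 result not tied to a reported diagnosis. No listed value and no adverse event count changes. The numerical examples rest on assumed normal ranges and on both excursions occurring in one subject. The absence of a metric and the loss of one direction rest on the text alone.

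**What to change.** Delete the furthest-value rule from SAP 8.1.2 and from the footnotes of Tables 14.3.4.4 and 14.3.4.5. Tabulate two shifts per parameter: baseline category to lowest post-baseline category, and baseline category to highest post-baseline category. Retitle the tables to match. A subject with both excursions then counts once in each block, as Low in the first and High in the second, and no distance is needed.

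The SAP has a precedent: for Day 0 vital signs, section 8.1.3 presents each subject's minimum and maximum rather than choosing between them. Defining the distance alone would make the tables reproducible but would still drop one direction.

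The cost is one extra column block per shift table and no new data.
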